2.2 Secondary Objective and Endpoint

Objectives	Endpoints
To assess the rate of surgical cure with and without pembrolizumab.	Proportion of patients who achieve a sustained complete response following second evacuation and no further anti-cancer therapy, defined as normalisation of hCG and no rise by 1 year post procedure.
To assess the safety of a single dose of pembrolizumab prior to second evacuation versus second evacuation alone.	Incidence of adverse effects of second evacuation and pembrolizumab within 30 days and 12 weeks respectively, assessed by Common Terminology Criteria for Adverse Events (CTCAE v5.0, 27 Nov 2017).

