6.11 Withdrawal from Study

Withdrawal from the study refers to discontinuation of study treatment and study procedures and can occur for the following reasons:

- Participant decision
- In the intervention arm, development of indications for urgent chemotherapy in the period between receiving pembrolizumab and awaiting second evacuation, discussed further below*

**Patients who develop vaginal bleeding, rising hCG >100,000 IU/L or any other indication for urgent chemotherapy will be withdrawn from the study to commence chemotherapy as determined by the treating team.*

(i) Procedures for Withdrawal from Study

In the event of a patient withdrawing from the study, no further visits or follow up will be conducted. The primary reason must be recorded in the eCRF and the patient's medical records. Any data and samples already collected will be retained and analysed.

Where the patient has withdrawn due to an AE, the investigator should follow the procedures in section 7.0.

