8. STATISTICAL ANALYSES

8.1 Sample Size and power considerations

8.1.1 Feasibility of the treatment strategy

A primary goal of the study is to determine the proportion of patients in the treatment arm who complete the planned protocol of pembrolizumab followed by second evacuation. To justify a larger study of this intervention, we would expect 90% of patients to complete the protocol with a lower bound of 70% below which we would not consider the strategy to be practicable. With 10 patients, assuming 90% complete protocol treatments, the 95% confidence interval is 71 – 100%.

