8.1.3 Detection of a clinical meaningful result

Given the challenges of carrying out definitive randomised controlled trials in the rare disease setting, data from small scale studies have been highly influential in driving treatment advances. The global adoption of pembrolizumab for GTN is a case in point. Our initial observation was exceptionally high pembrolizumab efficacy amongst a series of 4 patients. These data were sufficient to result in a change in NHS guidelines to support funding of this agent for patients with resistant disease. As we and the global community have accrued more data, use of pembrolizumab is now recommended in global GTN management guidelines.

While, as per recommendations for feasibility studies, we did not conduct sample size calculations for the pembrolizumab vs control comparison, we note that even with such a small sample size we would have adequate power to detect a clinically significant difference between the arms. Second evacuation for disease recurrence has a complete response (CR) rate of ~25% based on a study done at our centre. Amongst the remainder who relapse, we estimate a 75% CR rate to pembrolizumab based on multicentre data on patients with drug resistant, metastatic disease. We thus estimate the CR rate of neoadjuvant pembrolizumab to be 81% ($100*[0.25+(1-0.25)*0.75]$). For 80% power with α of 0.05, 9 patients per arm are required. This is consistent with 20 patients in total, randomised 1:1 to the control and neoadjuvant pembrolizumab arms.

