8.3 Statistical analysis

8.3.1 Analysis populations

In order to describe feasibility of the approach and collect tissue for translational activities, the primary analysis population will be Intention to Treat (ITT). To determine patient interest as a second measure of feasibility, we will additionally consider the population of patients assessed for eligibility

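### The supportive power statement in 8.1.3 (81% vs 25%, 9 per arm) holds only if every intervention-arm patient reaches second evacuation, while 8.1.1 works with 90% completion

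*Protocol*

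**What the plan says.** Protocol 8.1.3 starts from the control arm: "Second evacuation for disease recurrence has a complete response (CR) rate of ~25% based on a study done at our centre". It adds: "Amongst the remainder who relapse, we estimate a 75% CR rate to pembrolizumab". From these it builds 0.25 + 0.75 × 0.75 and states: "We thus estimate the CR rate of neoadjuvant pembrolizumab to be 81" per cent. It then says: "For 80% power with α of 0.05, 9 patients per arm are required", and calls this consistent with 20 patients randomised 1:1. The same paragraph says that no sample size calculation was done for this comparison, but that power for a clinically significant difference would nonetheless be adequate.

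Four other sections bear on this:

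- 8.1.1, on pembrolizumab followed by evacuation: "we would expect 90% of patients to complete the protocol", with 70% as the level below which the strategy would not be practicable.
- 2.2 defines cure as "sustained complete response following second evacuation and no further anti-cancer therapy", with hCG normal and no rise by one year.
- 6.11 lists as a reason for withdrawal: "In the intervention arm, development of indications for urgent chemotherapy in the period between receiving pembrolizumab and awaiting second evacuation". These patients start chemotherapy, and no further study visits follow.
- 8.3.1 makes intention to treat the primary analysis population, giving feasibility and tissue collection as the reason. It names no separate population for cure.

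**The concern.** The 81% combines two response probabilities for a patient who receives pembrolizumab and then has the evacuation. Two subsections earlier, the protocol works with one in ten intervention-arm patients not completing that sequence. Some of these patients cannot be counted as cured under 2.2: there is no second evacuation for a response to follow, or chemotherapy has been given. If they stay in the denominator, they can lower the intervention rate and shrink the difference that the power statement relies on. Having 10 patients per arm where 9 are needed does not settle this. Inflation replaces patients who are removed from the analysis, whereas failures kept in the denominator reduce the effect itself.

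At stake is how the cure comparison is read. Section 8.1.3 argues that small data sets have changed practice in this disease, and section 1.1 says the trial could directly set a new standard of care. A reader who takes the statement at face value would treat an inconclusive comparison as coming from a trial with at least 80% power.

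**Working it through.** **Inputs.** Control cure 25%, response to pembrolizumab among the remainder 75%, 80% power, α 0.05, 9 per arm (all 8.1.3). Completion 90%, floor 70% (8.1.1). Second stated size: 66% vs 25%, 40 in total (8.1.2). Planned 10 per arm (3.2).

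**Reproducing the protocol's figures.** The formula is not named. The two-sided normal approximation with unpooled variance is n per arm = (1.96 + 0.8416)² × [p₁(1−p₁) + p₂(1−p₂)] / (p₂−p₁)², where (1.96 + 0.8416)² = 7.849.

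- 25% vs 81.25%: 7.849 × (0.1875 + 0.1523) / 0.3164 = 8.43, so 9 per arm, as stated.
- 25% vs 66%: 7.849 × (0.1875 + 0.2244) / 0.1681 = 19.23, so 20 per arm and 40 in total, as stated in 8.1.2.

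A pooled one-sided version also gives 9 for the first case, but it gives 18 per arm (36 in total) for the second. Of the versions tried, only the unpooled two-sided one matches both, so it is used below.

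**Cure rate among all randomised at 90% completion.** Let f be the share of the 10% non-completers who would have been cured had they completed, and count non-completers as failures. The intervention rate is then 81.25% − 10% × f.

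- f = 0 (all would have failed anyway): 81.25%.
- f = 0.5: 76.25%.
- f = 0.8125 (non-completion unrelated to response): 73.125%, the same as 0.9 × 81.25%.

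**Size and power against 25%.** Power at 10 per arm is Φ(d/SE − 1.96), with d = p₂ − p₁ and SE = √{[p₁(1−p₁) + p₂(1−p₂)]/10}.

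| Intervention rate | n from formula | Per arm | Power at 10 per arm | Two-sided Fisher power at 10 per arm |
|---|---|---|---|---|
| 81.25% | 8.43 | 9 | Φ(3.05 − 1.96) = 86% | 56% |
| 76.25% | 11.01 | 12 | Φ(2.67 − 1.96) = 76% | 45% |
| 73.125% | 13.01 | 14 | Φ(2.46 − 1.96) = 69% | 38% |

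Power at 10 per arm reaches exactly 80% at an intervention rate of 78.1%, which is f = (81.25 − 78.06)/10 = 0.32. It falls below 80% once more than about a third of the non-completers would otherwise have been cured.

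**Other variations.**

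- Non-completers keep a 25% chance of cure: 0.9 × 81.25% + 0.1 × 25% = 75.6%, giving 12 per arm and 75% power.
- Control arm also reduced by a tenth (22.5% vs 73.1%): 12 per arm and 75% power.
- 95% completion, unrelated to response (77.2%): 11 per arm and 78% power.
- 70% completion, unrelated to response (0.7 × 81.25% = 56.9%): 34 per arm and 33% power.

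**The case against.** The strongest reply is that multiplying 81% by 0.9 may count the same failures twice. The withdrawal reasons in 6.11 are bleeding, a high rising hCG and other urgent indications for chemotherapy. These are largely signs of disease that is not responding, and the 81.25% already contains 18.75% failures. If all non-completers fall among those, the rate stays at 81.25% and 9 per arm is right. This stands. A reader might infer that the true requirement is 14 per arm, but the documents do not support that as a single answer. It needs non-completion to be unrelated to response, which the protocol does not say.

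Other points also stand in part:

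- A reader might say that every non-completer fails by definition. That is true of patients given chemotherapy or never evacuated. A patient who missed pembrolizumab but was evacuated and followed could still be cured.
- Applying intention to treat to cure is an inference. Section 8.3.1 justifies it for feasibility and tissue, and 8.3.3 sets a one-year landmark after evacuation without saying how non-evacuated patients count. That detail may properly sit in the SAP.
- The 90% is framed as a criterion for justifying a larger study. It is, however, the only completion rate the protocol works with, and 8.1.1 uses it for its own interval.
- Section 8.1.3 disclaims a formal calculation, cure is a secondary endpoint, and 8.1.1, 8.1.2 and 8.1.4 also support 20 patients. So the documents do not support the reading that the sample size is invalid. The disclaimer does not cover the claim of adequate power made in the same sentence.

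**Conclusion.** The point holds as a missing condition on a supportive statement. There is no arithmetic error. The 81% and 9 per arm describe patients who complete pembrolizumab and evacuation. For all randomised patients at 90% completion, the supportable statement is a range: cure of about 73% to 81%, a need of about 14 down to 9 per arm, and power of about 69% to 86% at 10 per arm. Overlap of half gives 76%, 12 per arm and 76% power.

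The range assumes a control rate of 25%, non-completers counted as failures, and the unpooled normal formula. Its lower end assumes that non-completion is unrelated to response; its upper end assumes that every non-completer would have failed anyway. With 10 per arm the normal approximation is generous: two-sided Fisher power over the same range is about 38% to 56%. The weight is moderate, because cure is secondary in a feasibility study, but as worded the power claim is not secured by the protocol's own completion figure.

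**What to change.** In 8.1.3:

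1. State that the 81% and the 9 per arm apply to patients who complete protocol treatment.
2. Add the range for all randomised patients at the planned 90% completion: cure of about 73% to 81%, and about 69% to 86% power at 10 per arm. Name the formula and say which assumption about non-completion gives each end.
3. Note that two-sided Fisher's exact test gives lower power, about 38% to 56%.
4. Remove the unqualified claim of adequate power.

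Keep 20 patients. The cost is one paragraph of wording and a less favourable stated power, with no extra patients and no change to treatment or conduct.

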8.1.4 Translation aims

A co-primary objective of the study is to obtain second evacuation tissue and blood for translational research. We have carried out sample size estimation to evaluate the number of patients required to identify immunotherapy triggered differences in the transcriptional profile of key tumour infiltrating T cell populations. Assuming 1000 genes are tested with average read count of 50, to identify 50 genes which are differentially expressed with a fold change of 4 or more at a false discovery rate (FDR) of 0.05, requires 9 patients per group (determined using the RnaSeqSampleSize package; Zhao 2018).

In summary, 10 patients per arm is justified to achieve the goals of this study.

8.2 Planned recruitment rate

Analysis of our current caseload reveals approximately 30 cases/year are eligible. We aim to enrol all patients within 12 months of opening and will determine

recruitment rates at a planned 6 month interim review. If recruitment targets are not met (<40% of patients recruited), we will open a second site at Weston Park Hospital (the only other centre for GTN management in England and Wales).

8.3 Statistical analysis

8.3.1 Analysis populations

In order to describe feasibility of the approach and collect tissue for translational activities, the primary analysis population will be Intention to Treat (ITT). To determine patient interest as a second measure of feasibility, we will additionally consider the population of patients assessed for eligibility

8.3.2 Primary Endpoint Analysis

We will carry out descriptive data analyses with respect to the feasibility of recruitment and completing protocolled treatments on the intervention arm.

Firstly, participant flows will be evaluated using a CONSORT diagram adapted for feasibility studies³⁸. We will record the numbers of patients:

1. With low risk GTN following primary evacuation of CHM
2. Consented
3. Screened
4. Eligible
5. Randomised
6. Who complete per protocol treatments

The number of patients who drop-out at each stage will additionally be recorded.

We will calculate the proportion of eligible patients who consent to participation as a measure of the potential to recruit to a larger study, along with the proportion of patients randomised to the intervention arm who complete per protocol treatments. In the intervention arm, the proportion of patients who are withdrawn from the study after pembrolizumab but before second evacuation and the reasons for this. The 95% confidence intervals will be calculated along with these proportions.

8.3.3 Secondary Endpoint Analysis

Recurrence free survival rate will be evaluated at the 1 year landmark post second evacuation. Safety data analysis will be conducted as below (8.3.4).

RESOLVE	C/43/2022	Imperial College London	v2.0 10 th July 2023
---------	-----------	-------------------------	------------------------------------

8.3.4 Safety Analysis

Safety data analysis will be conducted on all subjects randomised within the trial. Data will be collected on the number of patients who are withdrawn from the study in order to commence chemotherapy due to tumour progression. The number and proportion of patients who experience complications arising from second evacuation will be reported. In the intervention arm, the number and percentage of subjects experiencing an AE and the number of events will be reported. Information regarding severity will be examined with a focus on Grade 3-5 events using the Common Terminology Criteria for Adverse Events (CTCAE v5.0).

RESOLVE	C/43/2022	Imperial College London	v2.0 10 th July 2023
---------	-----------	-------------------------	------------------------------------

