3.2 Treatment regimens

Table 1: Summary of treatment groups

Treatment arm	Number of participants
Second evacuation alone (control)	10
Pembrolizumab followed by second evacuation (Intervention)	10
Total number of participants	20

Figure 1: Study Flowchart

Key:

CHM – Complete Hydatidiform mole; **1ry** – Primary; **CPI** – Checkpoint inhibitor; **Pembro** – Pembrolizumab; **FU** – Follow up Visit

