5.4 Randomisation

After eligibility has been confirmed, patients will be randomised to the trial. Randomisation will be performed centrally by Imperial Cancer Clinical Trials Section (CCTS) using the study database. There will be no option for manual randomisation. Upon randomisation each patient will be allocated a unique subject ID which should be used in all future correspondence. Please refer to the eCRF Completion Manual for further details on patient randomisation.

RESOLVE	C/43/2022	Imperial College London	v2.0 10 th July 2023
---------	-----------	-------------------------	------------------------------------

In this open-label study, randomisation will be on a 1:1 basis between second evacuation and pembrolizumab prior to second evacuation arms. Randomisation will be stratified according to baseline hCG since this has been shown to strongly influence the probability of cure following second evacuation. Based on historical data, we have carried out simulations to show that randomising patients within pre-defined hCG values corresponding to expected median or quartile limits results in balanced distribution of hCG values between the two arms in over 95% of simulated trials. The Trial Statistician will be responsible for holding the randomisation code securely until the final analysis of the study but also to enable the interim analysis.

After eligibility has been confirmed, an archival tissue sample in the form of formalin fixed paraffin embedded (FFPE) tumour block and/or diagnostic tissue section will be collected from each patient.

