The following laboratory evaluations will be conducted as indicated in the schedule of assessments tables, with collection and analysis according to standard practice at the relevant site.

- **Haematology:** White blood cell count (WBC) with differential, haemoglobin (Hgb), haematocrit (Hct) and platelet count.
- **Biochemistry:** Chem 7 (sodium [Na], potassium [K], chloride [Cl], bicarbonate [CO₂], creatinine [Cr], glucose), calcium, phosphate, magnesium, urea and electrolytes. Creatinine clearance calculated based on Cockcroft-Gault estimate.
- **Liver function tests (LFTs):** ALT or AST (either or both as per local practice), alkaline phosphatase (ALP), albumin, lactate dehydrogenase (LDH) and total bilirubin.
- **Coagulation screen:** APTT, PT
- **Thyroid function tests (TFTs):** TSH, free T3, free T4.
- **Viral Screen:** Hepatitis B, Hepatitis C and Human Immunodeficiency virus (HIV)
- Human Chorionic Gonadotropin (hCG) blood or urine test

(vii) Tumour assessment

Tumour assessment will be performed by serial hCG measurement. Complete response is defined as normalisation of hCG levels (<5 IU/L) post second evacuation.

(viii) Thoracic x-ray and uterine ultrasound Scan (USS)

A thoracic x-ray and uterine ultrasound scan (USS) will be undertaken as part of pre-screening to ascertain if disease is low or high risk. The USS will be transvaginal, unless adequate imaging to determine eligibility criteria can be obtained by a transabdominal scan.

Additionally, a second uterine USS will be undertaken prior to second evacuation to ensure the disease remains amenable to second evacuation (disease within the uterine cavity and not within 5mm of the serosal surface). The second scan will routinely be carried out as a transvaginal study.

For the Pembrolizumab arm only, two optional MRI scans may be performed (funding permitted); the first of which would be given during the screening period and the second within two days before the second evacuation visit. The MRIs will be used for exploratory analysis separate from the main study.

(ix) Assessment of adverse events

Adverse events will be assessed as indicated in the schedule of assessments table, according to the data detailed in section 7.1.

(x) Assessment of concomitant medications

Concomitant medications will be assessed as indicated in schedule of assessments table, with the following data recorded for each medication:

- Name
- Start date / whether ongoing / end date
- Indication
- Dosage
- Frequency

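### Safety is analysed on all randomised patients, so patients never evacuated or never dosed count as free of the corresponding harm; the expected understatement is small and falls mainly on the intervention arm

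*Protocol*

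**What the plan says.** Section 8.3.4 of the protocol opens with the population: "Safety data analysis will be conducted on all subjects randomised within the trial". It then promises, for the procedure, "The number and proportion of patients who experience complications arising from second evacuation will be reported", and for the intervention arm the number and percentage of subjects with an adverse event. No second denominator appears.

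The endpoint in section 2.2 is specific to each exposure: adverse effects of the evacuation within 30 days and of pembrolizumab within 12 weeks. The objective attached to it compares pembrolizumab before evacuation with evacuation alone.

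The protocol foresees patients who are randomised but not evacuated:

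- Section 6.11 lists as a reason for withdrawal "In the intervention arm, development of indications for urgent chemotherapy in the period between receiving pembrolizumab and awaiting second evacuation". It also lists "Participant decision", with no arm named.
- Section 5.8 states that "a second uterine USS will be undertaken prior to second evacuation to ensure the disease remains amenable to second evacuation". Tables 2 and 3 schedule this scan in both arms.
- Section 8.1.1 gives the expected completion and the floor for practicability: "we would expect 90% of patients to complete the protocol with a lower bound of 70% below which we would not consider the strategy".
- Section 8.3.2 plans to report the proportion withdrawn between pembrolizumab and evacuation in the intervention arm, with reasons.

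**The concern.** A patient who never undergoes the procedure is not at risk of its complications, and a patient who never receives the drug is not at risk of its adverse effects. Keeping such patients in the denominator lowers the proportion without lowering anyone's risk. The 30-day and 12-week windows in section 2.2 are most naturally read as starting at the procedure and at the dose, so these patients have no window in which an event could be counted.

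The comparison suffers only if the arms differ in how many patients miss the evacuation. The urgent-chemotherapy route gives a reason to expect more misses in the intervention arm. The arm with the added drug would then show a lower evacuation complication rate partly because fewer of its patients had the procedure, and the more patients the strategy loses before evacuation, the stronger the effect. Whether pembrolizumab makes the evacuation less safe is part of the secondary safety objective, and the results are meant to inform a larger study.

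**Working it through.** **Inputs**

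- Randomised: 10 per arm. Section 3.2, Table 1, row "Pembrolizumab followed by second evacuation (Intervention"), gives 10, and section 5.4 confirms that "randomisation will be on a 1:1 basis between second evacuation and pembrolizumab prior to second evacuation arms".
- Completion of pembrolizumab plus evacuation: 90% expected, 70% as the practicability floor (section 8.1.1).
- Background harm of second evacuation (section 1.4.3): four grade 1 and one grade 3 haemorrhage and one perforation among 134 patients. If these were six different patients (an assumption), the rate is 6/134 = 4.5%.

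**The protocol's own figure**

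The only related figure is the interval for completion in section 8.1.1. With p = 0.9 and n = 10, p ± 1.96 × √(p(1 − p)/n) = 0.9 ± 0.186, or 71.4% to 108.6%. Cut at 100%, this gives the stated 71–100%. The protocol gives no numerical safety rate to reproduce.

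**Dilution factor**

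Let N be the number randomised to an arm, k the number evacuated and x the number with a complication. Then

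x/N = (x/k) × (k/N).

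The reported proportion is the proportion among those evacuated times k/N. If every non-completer misses the evacuation, k/N is 9/10 = 0.9 at 90% completion and 7/10 = 0.7 at the floor.

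| Evacuated, of 10 | One event: x/k | One event: x/10 | Two events: x/k | Two events: x/10 |
|---|---|---|---|---|
| 9 | 11.1% | 10.0% | 22.2% | 20.0% |
| 8 | 12.5% | 10.0% | 25.0% | 20.0% |
| 7 | 14.3% | 10.0% | 28.6% | 20.0% |

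**At the background rate**

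- 90% completion: 4.5% × 0.9 = 4.0%.
- 70% completion: 4.5% × 0.7 = 3.1%.

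The fall is at most about 1.3 percentage points (4.48 − 3.13). Among seven evacuated patients, 7 × 0.0448 = 0.3 events would be expected.

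**How often it would arise**

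The chance that at least one of 10 intervention patients does not complete is 1 − 0.9^10 = 65% at 90% completion, 1 − 0.8^10 = 89% at 80% and 1 − 0.7^10 = 97% at 70%.

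**Effect on the comparison**

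With 10 randomised to each arm and equal true risk among those evacuated, the expected ratio of reported rates (intervention to control) is k_I/k_C. It is 9/10 = 0.9 if only one intervention patient misses the evacuation, 9/9 = 1.0 if one patient in each arm does, and 7/10 = 0.7 if three intervention patients and no control patient do. The comparison is distorted by the imbalance in misses, while each arm's own rate is diluted by its own misses.

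**The case against.** **The population sentence does not write out the fraction.** Section 8.3.4 names a population and leaves the numerator and denominator of each table unwritten; table detail is commonly left to the statistical analysis plan. This is true of the layout. But one population is named, a proportion is promised under it, and the plain reading is x over all randomised. An analysis plan using only exposed patients would depart from that text.

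**A reader might infer that dilution occurs only in the intervention arm.** The documents do not support that. Participant decision and the scan before evacuation apply to both arms, the footnote on urgent chemotherapy in section 6.11 names no arm, and section 9.11 lets the clinician give alternative treatment at any stage. What stands is an expectation: the listed urgent-chemotherapy route is an intervention-arm one, so more misses are likely there.

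**A reader might also infer that the intervention arm would typically look 30% safer.** That is the worst case. It requires completion at the floor, every non-completer missing the evacuation, and no control patient missing it. A patient who misses pembrolizumab but is evacuated is a non-completer who properly stays in the evacuation denominator.

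**All-randomised is a defensible choice.** It preserves the randomised comparison of strategies. Restricting to evacuated patients conditions on something that happens after randomisation, and those removed are the ones with bleeding, rising hCG or other indications for chemotherapy. The remaining subset may be at lower risk and could itself look too safe. This stands, and is why the all-randomised table should stay.

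**The loss is partly recoverable.** Counts are reported as well as proportions, and section 8.3.2 reports intervention-arm withdrawals before evacuation. But its participant flow counts those who complete treatment per protocol, which is not the number evacuated in each arm.

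**Undosed patients should be few.** Table 3 places randomisation within days −3 to 0 and the dose on day 0, so dilution of the pembrolizumab percentage is possible but probably slight.

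**Conclusion.** The concern holds as a minor one. Followed as written, section 8.3.4 understates the evacuation complication rate in any arm where a patient misses the evacuation, and the pembrolizumab adverse event percentage if any patient is not dosed. In the intervention arm the factor is about 0.9 at the expected completion and 0.7 at the practicability floor; lower completion would reduce it further, but the protocol would by then regard the strategy as not practicable. At the background rate this turns about 4.5% into 4.0%, or 3.1% at worst.

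The size rests on four assumptions: non-completion means no evacuation; the six background events were in different patients; the background rate carries over to this trial; and the proportion is shown by arm, which section 8.3.4 does not say but the comparative objective implies. The direction rests on more intervention than control patients missing the evacuation, which is likely but not certain. With 10 per arm and a descriptive analysis, no safety table could resolve a difference of this size. The reason to act is that the reported rate should match the endpoint.

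**What to change.** In section 8.3.4, state that complications of second evacuation are reported by arm among patients who underwent it, and adverse effects of pembrolizumab among patients who received the dose. Keep the all-randomised table beside these as the summary of the two treatment strategies, and give the number evacuated in each arm and the number dosed. Add that the evacuated subset is selected after randomisation and may be at lower risk, so its comparison between arms is descriptive.

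The cost is a sentence or two in the protocol and one more column in the safety table. No new data are needed.
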